Abbreviated Title: Prostvac-Nivo in prostate ca

Version Date: 01.10.2023

Abbreviated Title: Prostvac-Nivo in Prostate CA

NIH Protocol #: 17-C-0007

IBC #: RD-16-VI-02

Version Date: January 10, 2023

NCT #: NCT02933255

Title: Phase I/II Study of PROSTVAC in Combination with Nivolumab in Men with Prostate Cancer

NCI Principal Investigator:

[name], PhD
Genitourinary Malignancies Branch (GMB)
Center for Cancer Research (CCR)
National Cancer Institute (NCI)
[name]
[name]
[name]
[REDACTED]

Drug Name	PROSTVAC-V/F	Nivolumab (BMS-936558, MDX-1106, and ONO-4538) (NSC 748726)
IND Number	17104	17104
Sponsor	CCR, NCI	CCR, NCI
Manufacturer	Bavarian Nordic, Inc.	Bristol-Myers Squibb
Supplier	Bavarian Nordic, Inc.	Bristol-Myers Squibb

PRÉCIS

Background:

- Immune checkpoint inhibitors interfere with the immune system's autoregulatory mechanisms, allowing for a potentially expanded and prolonged T-cell response with the possibility of greater antitumor effects.
- Nivolumab is a fully human IgG4 monoclonal antibody that targets the PD-1 protein. Specifically, the antibody binds to the PD-1 receptor and blocks its interaction with PD-L1 and PD-L2, thereby releasing PD-1 pathway-mediated inhibition of the immune response, including anti-tumor immune response.
- PROSTVAC (developed by the National Cancer Institute [NCI] and licensed to Bavarian Nordic Immunotherapeutics, Mountain View, CA) is a therapeutic cancer vaccine for prostate cancer. Early studies have demonstrated immunologic efficacy and suggested clinical benefit. A phase III trial has completed accrual.
- A previous study combining the immune checkpoint inhibitor ipilimumab and PROSTVAC suggested greater efficacy than PROSTVAC alone. Additional studies have demonstrated the potential efficacy of immunologic combination therapy with the immune checkpoint inhibitor nivolumab.
- This study will aim to evaluate the impact of the combination of PROSTVAC and the immune checkpoint inhibitor nivolumab on the tumor microenvironment focusing on immune cell infiltration as the primary endpoint.
- US-MRI imaging technology will be employed to sample the tumor before treatment and after radical prostatectomy.
- The findings from this study could serve as the basis for future studies with this combination in this population of participants and more advanced disease.

Objectives:

- Safety (For castration resistant prostate cancer (CRPC) lead-in cohort)
- Evaluate changes in T-cell infiltration in the tumor after neoadjuvant treatment with PROSTVAC and nivolumab, relative to changes seen in a phase 2 trial with PROSTVAC alone in the neoadjuvant setting- NCT02153918 (For the neoadjuvant cohort).

Eligibility:

- Participants must have histopathological documentation of adenocarcinoma of the prostate prior to starting this study and evaluable biopsy tissue (e.g., unstained slides or blocks) available for analysis.
- For the castration resistant lead in cohort, if histopathological documentation is unavailable, a rising PSA and a clinical course consistent with prostate cancer would be acceptable.
- Participants must have a performance status of 0 to 1 according to the ECOG criteria.
- Hematological eligibility parameters (within 16 days of starting therapy):

Abbreviated Title: Prostvac-Nivo in prostate ca

Version Date: 01.10.2023

- Granulocyte count 1,500/mm³
- Platelet count 100,000/mm³
- Hgb \geq 8 g/dL
- Biochemical eligibility parameters (within 16 days of starting therapy):
- Hepatic function: Bilirubin $<$ 1.5 mg/dl (OR in participants with Gilbert's syndrome, total bilirubin \leq 3.0 mg/dL), AST and ALT \leq 2.5 times upper limit of normal.
- Creatinine \leq 1.5 X ULN

Design:

- The primary focus of this study will be to evaluate PROSTVAC and nivolumab in the neoadjuvant setting.
- Lead-in cohort evaluating the safety and tolerability of this combination in the castration resistant setting (CRPC cohort)
- Following this lead-in cohort in the CRPC setting, we will enroll a cohort in the neoadjuvant setting evaluating the combination of PROSTVAC and nivolumab.
- The lead-in safety cohort will require 10 participants and the neoadjuvant cohort will require 17 evaluable participants. In order to allow for a small number of inevaluable participants, the accrual ceiling will be set to 29 participants.

TABLE OF CONTENTS

PRÉCIS.....	2
TABLE OF CONTENTS	4
STATEMENT OF COMPLIANCE	7
1 INTRODUCTION	7
1.1 Study Objectives	7
1.2 Background and Rationale	8
2 ELIGIBILITY ASSESSMENT AND ENROLLMENT	18
2.1 Eligibility Criteria	18
2.2 Participant Registration and Status Update Procedures.....	22
2.3 Baseline Evaluation.....	23
3 STUDY IMPLEMENTATION	24
3.1 Study Design	24
3.2 Drug Administration	25
3.3 Dose Modifications	26
3.4 Stopping Rules	26
3.5 Study Calendar.....	28
3.6 Cost and Compensation	34
3.7 Criteria for Removal from Protocol Therapy and Off Study Criteria.....	34
3.8 Follow-up Evaluations	35

The trial will be carried out in accordance with International Conference on Harmonisation Good Clinical Practice (ICH GCP) and the following:

- United States (US) Code of Federal Regulations (CFR) applicable to clinical studies (45 CFR Part 46, 21 CFR Part 50, 21 CFR Part 56, 21 CFR Part 312, and/or 21 CFR Part 812)

National Institutes of Health (NIH)-funded investigators and clinical trial site staff who are responsible for the conduct, management, or oversight of NIH-funded clinical trials have completed Human Subjects Protection and ICH GCP Training.

The protocol, informed consent form(s), recruitment materials, and all participant materials will be submitted to the Institutional Review Board (IRB) for review and approval. Approval of both the protocol and the consent form must be obtained before any participant is enrolled. Any amendment to the protocol will require review and approval by the IRB before the changes are implemented to the study. In addition, all changes to the consent form will be IRB-approved; an IRB determination will be made regarding whether a new consent needs to be obtained from participants who provided consent, using a previously approved consent form.

1 INTRODUCTION

1.1 STUDY OBJECTIVES

1.1.1 Primary Objective

- Safety (For castration resistant prostate cancer (CRPC) lead-in cohort)
- Evaluate changes in T-cell infiltration in the tumor after neoadjuvant treatment with PROSTVAC and nivolumab, relative to changes seen in a phase 2 trial with PROSTVAC alone in the neoadjuvant setting – NCT02153918 (For neoadjuvant cohort).

1.1.2 Secondary Objectives

- To determine the change in peripheral PSA-specific T cells in participants treated with PROSTVAC and nivolumab.
- To document any intraprostatic T_{reg} cell infiltration with CD4+FOX-P3 staining.
- To document any PSA changes secondary to immune treatment, including rate of biochemical recurrence after prostatectomy.
- To document any MRI changes secondary to treatment (including changes in ADC mapping)
- To evaluate changes in PDL-1 expression in tumor.
- To document pathologic responses (including pathologic CR).
- To evaluate changes in immune cell subsets in the periphery.
- To evaluate changes in soluble immune mediating factors (such as cytokines, etc.) in sera.
- To evaluate changes in circulating tumor cells levels (for CRPC cohort only)
- Safety (for localized prostate cancer cohort)

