1.2 BACKGROUND AND RATIONALE

It is expected that 26,120 men will die from prostate cancer in the US in 2016.[1-3] While some men are definitively treated for localized disease, many men will ultimately develop castrate resistant prostate cancer (CRPC) and succumb to the disease;² this is due to the lack of an optimal treatment strategy. Treatment options typically involve radical prostatectomy (RP) or radiation therapy (RT) in combination with androgen deprivation therapy (ADT). Following RP upwards of 50% of patients with high-risk disease will experience a biochemical recurrence at 5 years, [4] and approximately 20% will die of their disease in 10-15 years. [5]

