2.2.1 Treatment Assignment Procedures

Cohorts

Number	Name	Description
1	Cohort 1	Men with Prostate Cancer

Arms

Number	Name	Description
1	Lead-in CRPC Cohort	PROSTVAC-V on week 0 followed by booster injection called PROSTVAC-F on 2, 4, and 8 weeks. Nivolumab will be administered every 2 weeks, starting at week 2. When administered on the same day, the preferred order of administration is PROSTVAC first followed by nivolumab. Participants will undergo restaging scans on week 12 prior to receiving treatment. If no PD, option to continue treatment with nivolumab every 2 weeks and PROSTVAC-F every 4 weeks until intolerance or progression (evaluated radiographically every 12 weeks). Participants who remain on protocol beyond 1 year will have the option of extending the nivolumab dosing interval to every 4 weeks.
2	Neoadjuvant Cohort	PROSTVAC-V on week 0 followed by booster injection called PROSTVAC-F on 2, 4 and 8 weeks. Nivolumab will be administered on weeks 2, 4, 6, and 8. When administered on the same day, the preferred order of administration is PROSTVAC first followed by nivolumab. Participants will undergo prostatectomy on week 9. (If surgery is scheduled earlier than 9 weeks after initial dosing, the 6 and 8 week dosing may be skipped and surgery may be done as early as week 5.)

Arm Assignment

Participants in cohort 1 will be assigned to arm 1 until the expected number of participants enrolled (n=10), then participants will be assigned to arm 2 (n=17).

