3.1.2 Study Schema

Lead-in CRPC Cohort for safety:

	Week 0	Week 2	Week 4	Week 6	Week 8	Week 10	Week 12
N = 10	PROSTVA C-V	PROSTVA C-F Nivolumab	PROSTVA C-F Nivolumab	Nivolumab	PROSTVA C-F Nivolumab	Nivolumab	Restaging CT and Bone scan and if no PD option to continue treatment until intolerance or progression (evaluated radiographically every 12 weeks)

PROSTVAC-V 2×10^8 Infectious Units

PROSTVAC-F 1×10^9 Infectious Units

Nivolumab 240 mg (Flat dose) every 2 weeks. Alternately, participants who remain on protocol beyond 1 year may transition to nivolumab 480 mg (flat dose) every 4 weeks.

Neoadjuvant Cohort:

	Week 0	Week 2	Week 4	Week 6*	Week 8*	Week 9*
N=17	PROSTVAC-V	PROSTVAC-F Nivolumab	PROSTVAC-F Nivolumab	Nivolumab	PROSTVAC-F Nivolumab	Prostatectomy

PROSTVAC-V 2×10^8 Infectious Units

PROSTVAC-F 1×10^9 Infectious Units

Nivolumab 240 mg (Flat dose)

*If surgery is scheduled earlier than 9 weeks after initial dosing, the 6 and 8 week dosing may be skipped and surgery may be done as early as week 5.

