3.8 FOLLOW-UP EVALUATIONS

After subjects have stopped taking the study medication for any of the reasons listed in Section **3.6**, they will be seen at NIH, if logistically feasible, for a safety visit within 4-5 weeks for Lead-in mCRPC cohort and 6-8 weeks for neoadjuvant cohort of drug discontinuation. The safety assessments may be performed by a local physician and laboratory if participants unable to return to the NIH Clinical Center at this time.

The following assessments will be performed at the follow up safety visit:

- History and Physical Examination
- CBC with differential and platelet count, prothrombin time/INR, activated partial thromboplastin time
- Serum chemistries (Na+, K+, Cl-, CO2, BUN, creatinine, glucose, AST/ALT, bilirubin, calcium, phosphorous, albumin, magnesium, alkaline phosphatase, LDH, ionized calcium, amylase, lipase, total protein, uric acid), TSH
- Serum PSA level
- Adverse event reporting

After the safety visit, if there are no unresolved grade 3 or higher AEs, we will offer participants the opportunity to enroll on our long term follow up study. If there are unresolved grade 3 – 4 AEs, participants will be followed either at the NIH Clinical Center or by their local physician. In the latter case, we will obtain the physician's record of AEs.

Any scans performed outside of the NIH will also be obtained when possible.

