3.9 POST-STUDY EVALUATION

In 2006, the FDA excluded pox virus based vaccine platforms from required long term follow-up. Following this guidance in 2006 we haven't built in long term follow-up for our pox-viral studies as such vectors have not been shown to have a propensity to integrate or reactivate following latency and, in the absence of evidence to the contrary, present a low risk of gene therapy-related delayed adverse events. Therefore no long term follow up is required with this study, though participants will be offered the opportunity to enroll on our long term follow up study.

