4 CONCOMITANT MEDICATIONS/MEASURES

Subjects must inform the investigators of the current or planned use of all other medications during the study (including prescription medications, vitamins, herbal and nutritional supplements, and over-the-counter medications).

Anti-emetics, stool softeners and antidiarrheal agents may be administered as required but are not anticipated to be needed and should not be used prophylactically on the first cycle. The selection of the specific antiemetic regimen is at the discretion of the treating physician. Antiemetic regimens will not include steroids.

Other supportive care with blood components, antibiotics, analgesics, general medical therapy, etc., will be delivered as required. Any participants taking antibiotics for an active infection must complete that course of therapy and be free of evidence of further infection before receiving any immunotherapy treatment. Antibiotics for prophylaxis are allowed while on treatment.

Concurrent systemic corticosteroid use (daily or every other day for continued use > 14 days) should be avoided within 14 days before the first planned dose of PROSTVAC. Use of inhaled steroids, nasal sprays, and topical creams for small body areas is allowed. Limited use of steroids is allowed on study (e.g., for immune related adverse events or for premedication for imaging).

Symptomatic anemia should be treated with appropriate red blood cell or erythropoietin support.

Thrombocytopenia should be treated conservatively. In the absence of bleeding or a planned invasive procedure, platelet transfusions should be given for a platelet count below 10,000/mm³. If invasive procedures are planned or the participant develops bleeding, platelet transfusions should be administered in accordance with the standard of practice, usually maintaining a platelet count of > 50,000/mm³.

Any evidence of disseminated intravascular coagulation (DIC), hemolytic uremic syndrome (HUS), or thrombotic thrombocytopenic purpura (TTP) including thrombocytopenia, hemolytic anemia, renal failure, fever or neurologic changes should be thoroughly evaluated and closely monitored and supported as clinically indicated.

A standard of care radical prostatectomy will be performed between week 5 and week 12 to allow for logistical constraints, but ideally as close to week 9 as possible. This may occur at NIH or at an outside institution. Surgical specimens will be requested for research use (Section 5).

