With 17 total evaluable participants having both CD3+/CD4+ and CD3+/CD8+ T cell measurements from baseline to 9 weeks on the present trial, and comparable data from 26 participants on the 14-C-0112 trial, there would be adequate participants to have 80% power to detect a difference between the cohort from this trial and that from the prior trial of a change in each type of CD3+ T cells from baseline to 9 weeks (or baseline to 12 weeks in the 14-C-0112 trial) equal to 1.0 SD of the change in the CD3 + T cells (1.0 SD effect size) using a 0.025 significance level two-tailed two group t-test to allow adequate participants for a Bonferroni adjustment holding the overall significance level to 0.05 for both tests. In practice, a Hochberg adjustment may be used instead of the overly stringent Bonferroni adjustment. Also, if the distributions of the CD3 + T cells are not normally distributed ($p < 0.05$ by a Shapiro-Wilks test), then a Wilcoxon rank sum test may be used instead of a two-sample t-test. The results from the

comparison of data from the two studies will be reported with appropriate caveats to reflect differences in study characteristics, and to reflect the lack of randomized participant assignment between the two trials.

Secondary objectives are to determine the change in peripheral PSA-specific T cells in participants treated with these vaccines; to document any intraprostatic Treg cell infiltration with CD4+FOX-P3 staining; to document any PSA changes secondary to vaccination, including rate of biochemical recurrence after prostatectomy; to document any MRI changes secondary to treatment; to evaluate changes in PDL-1 expression; and to document pathologic responses (including pathologic CR). When analysis is required, each of these endpoints will be analyzed using appropriate nonparametric methods when applicable and the results from these analyses will be presented without formal adjustment for multiple comparisons, but in the context of the number of such evaluations undertaken.

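### Biochemical recurrence rate after prostatectomy is a secondary endpoint, but the protocol plans at most one post-operative PSA, about 2 to 7 weeks after on-schedule surgery, and names no other data source

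*Combined protocol and SAP*

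**What the plan says.** **Endpoint.** Section 1.1.2 lists as a secondary objective "To document any PSA changes secondary to immune treatment, including rate of biochemical recurrence after prostatectomy". Section 10 carries it into the statistical plan as "including rate of biochemical recurrence after prostatectomy". Its only method is a general reference to suitable nonparametric analysis of the secondary endpoints. I found no definition of recurrence for the surgical cohort, no time point and no time-to-event method.

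**Dosing and surgery.** For the neoadjuvant cohort, Section 2.2.1 states: "Nivolumab will be administered on weeks 2, 4, 6, and 8". Section 3.1.2 adds that, when surgery is scheduled early, "the 6 and 8 week dosing may be skipped and surgery may be done as early as week 5". Section 4 says that prostatectomy "will be performed between week 5 and week 12 to allow for logistical constraints, but ideally as close to week 9 as possible", at NIH or elsewhere. Section 3.7.1 removes a participant from therapy for late surgery only if the delay exceeds three months from week 12.

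**PSA after surgery.** Section 3.8 brings participants back "for a safety visit within 4-5 weeks for Lead-in mCRPC cohort and 6-8 weeks for neoadjuvant cohort of drug discontinuation" and lists a PSA among the assessments. The neoadjuvant calendar (Section 3.5.2) also includes PSA in the laboratory panel at that visit. The later contact, at about 100 days, is for serious adverse events and may be by phone.

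**After that.** Section 3.9 concludes: "Therefore no long term follow up is required with this study". Sections 3.8 and 3.9 offer participants a separate long-term study, and under Section 3.7.2 agreeing to be followed there is a ground for going off study.

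**The concern.** A recurrence rate needs a definition, a clock that starts at surgery, and PSA measurements long enough and often enough to see events. The plan promises the rate but schedules almost none of this. Section 1.2 itself puts recurrence on a scale of years: "upwards of 50% of patients with high-risk disease will experience a biochemical recurrence at 5 years". A proportion seen over a few weeks is not comparable with that figure.

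Two things are at stake. First, the objective cannot be answered from the data that the protocol schedules, even if every visit takes place. Second, Section 1.2.6 says the tissue findings could support a larger trial of cure rate or time to recurrence. A count such as 0/17, reported without its follow-up time, could be taken as support for that step. With no definition fixed in advance, the count would also depend on choices made after the data are seen, such as how to treat a PSA that never became undetectable.

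**Working it through.** The documents give no recurrence rate, power or precision for this endpoint, so there is no stated figure to reproduce.

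**Step 1: time from surgery to the last PSA.** Inputs are the dosing weeks (2.2.1, 3.1.2), surgery weeks (4), tolerated delay (3.7.1) and safety visit (3.5.2, 3.8). Formula: (last-dose week + 6 to 8) − surgery week.

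| Last dose | Surgery | Last PSA, weeks after surgery |
|---|---|---|
| week 8 | week 9 | 14−9 to 16−9 = 5 to 7 |
| week 8 | week 12 | 14−12 to 16−12 = 2 to 4 |
| week 4 | week 5 | 10−5 to 12−5 = 5 to 7 |
| week 4 | week 8 | 10−8 to 12−8 = 2 to 4 |
| week 4 | week 12 | 10−12 to 12−12 = −2 to 0 |
| week 8 | about week 25 (12 + 13) | 14−25 to 16−25 = −11 to −9 |

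The first four rows are on-schedule cases and give 2 to 7 weeks. The last two are an early stop of dosing and a delay up to the Section 3.7.1 limit. In those cases no scheduled PSA follows surgery.

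The post-treatment visit also includes a PSA, one week after the last planned dose with a window of −3 to +7 days. Its MRI is described in Section 5.1.4 as part of the pre-operative workup, so I do not count it as post-operative. If it slipped past a week-9 operation, it would fall at most about a week after it.

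**Step 2: could other text supply PSA values?**
- Section 6.3.6.1 has PSA every 12 weeks after treatment, but Section 6.3 is headed as applying to the CRPC cohort. Its progression rule is tied to PSA before and during androgen deprivation, which does not fit these men.
- The contact at about 100 days lists no PSA.
- The long-term study is optional, and no text says its data come back to this endpoint.

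**Step 3: expected recurrence in that window.** Inputs: 50% at 5 years (Section 1.2, high-risk disease; the cohort is not restricted to high risk) and 17 evaluable men (Section 10). The constant hazard is an assumption.

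h = −ln(1 − 0.50)/5 = 0.1386 per year; p(t) = 1 − exp(−h·t).

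- 2 weeks (t = 14/365.25): p = 0.5%; 17p = 0.09 events; chance of no event (1 − p)^17 = 91%.
- 7 weeks (t = 49/365.25): p = 1.8%; 17p = 0.31 events; chance of no event 73%.

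**Step 4: sensitivity (assumed values).**
- Lower 5-year risk: 30% gives 0.3% and 0.9% at 2 and 7 weeks; 20% gives 0.2% and 0.6%.
- Front-loaded hazard, 50% at 5 years, p(t) = 1 − exp(−ln 2·(t/5)^k): k = 0.7 gives 2.3% and 5.4%; k = 0.5 gives 5.9% and 10.7%, the last being 17 × 0.107 = 1.8 events.

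**Step 5: precision.** With 0/17, the exact two-sided 95% upper limit is 1 − 0.025^(1/17) = 19.5%.

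**Step 6: longer follow-up, for comparison.** On the constant-hazard 50% assumption, one year gives 12.9% (2.2 events in 17), two years 1 − 0.5^(2/5) = 24% (about 4 events), and five years 50% (8.5 events).

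**The case against.** **The consequence is small.** This is one clause of one of ten secondary objectives, and the verb is to document. Section 10 attaches no hypothesis, power or decision rule to it, and the primary endpoint and safety rule are untouched. A confidence interval on 0/17 would itself show how little is known. All of this stands, and it limits the weight of the point. It does not remove it: following the schedule exactly still leaves the objective unanswered.

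**The long-term study may hold the data.** Participants will be offered it, and its content cannot be seen from here. This also stands. What can be said is that the protocol does not state how recurrence data reach the analysis. The gap might be closed by a sentence rather than a redesign.

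**A stronger reading is tempting but not supported.** A reader might infer that the reported rate must be near zero by construction. That needs a constant hazard, yet an assumed front-loaded one gives about 5% to 11% at 7 weeks. It also needs a definition that leaves out persistent post-operative PSA, and the protocol has no definition. And it presumes that no long-term data are used, on which the documents are silent.

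**Longer follow-up would still be imprecise.** At two years, 4/17 would have an exact 95% interval of 6.8% to 49.9%, and no comparator is planned for this endpoint. This is correct, and is a reason to report any estimate as descriptive.

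**Conclusion.** The concern holds. A recurrence rate is a stated secondary endpoint, but the protocol plans at most one PSA after surgery, about 2 to 7 weeks after an on-schedule operation and possibly none after an early stop or a delay. A definition that requires a confirmatory value could not be met from scheduled data.

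The conclusion on timing rests only on the protocol's own schedule. The size rests on assumptions: 0.5% to 1.8% (0.1 to 0.3 events in 17) under a constant hazard at the protocol's high-risk figure, less if the cohort's risk is lower, and up to about 11% under a strongly front-loaded hazard. Across that range the result is uninformative about recurrence. The matter deserves correction, but it does not affect the primary analysis.

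**What to change.** Choose one of two routes.

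1. Remove the rate of biochemical recurrence from Section 1.1.2 and Section 10, keeping the objective on PSA changes. This costs almost nothing beyond the amendment.
2. Keep it and make it estimable:
   - define recurrence, including how persistent post-operative PSA is classified and whether a confirmatory value is needed;
   - name the data source, either standard-of-care post-operative PSA abstracted from local records or a stated link to the long-term follow-up study;
   - prespecify a horizon, chosen and justified by the sponsor;
   - report a Kaplan-Meier estimate timed from prostatectomy, with its confidence interval and the follow-up time, as descriptive only.

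The second route costs a short amendment, possible re-consent (some men may already be off study, and the IRB decides whether new consent is needed) and record abstraction for about 17 men. The estimate will remain imprecise. Neither route changes treatment.
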